		
Adherence will be measured as 'Proportion of days covered = (Number of days covered by any ART, excluding ritonavir and cobicistat) ÷ (total days)*100'[27] every six months
 
Individuals with >80% of days covered will be classified as 'adherent' and individuals with ≤80% of days covered will be classified as 'non-adherent'[27]
	
	CD4 cell count	Categorized as <200, 200-499, ≥500 cells/mm ³	Baseline and follow-up
	PPSV23 vaccination	NDC and CPT codes listed in Appendix Table 8	Baseline and follow-up
	Annual CD4 laboratory test	
CD4 laboratory tests will be identified by CPT codes listed in Appendix Table 9
 
Individuals who have at least one CD4 laboratory test performed during each year of follow-up
	Baseline and follow-up
	Annual viral load laboratory test	
Viral load laboratory tests will be identified by CPT codes listed in Appendix Table 10
 
Individuals who have at least one viral load laboratory test performed during each year of follow-up
	Baseline and follow-up
	Respiratory virus season	Respiratory virus season occurs between October 1 and April 30	Follow-up
Sensitivity analysis outcome	All-cause pneumonia not associated with HIV	ICD-9-CM or ICD-10-CM codes listed in Appendix Table 11	Follow-up

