### 5.3.2. Covariates

The list of demographic and clinical characteristics considered for descriptive reporting, subgroups and inclusion as covariates in models for generating the propensity scores are provided in Table 5.3. The Komodo Health database will be source of all variables.

Patients will be considered to have a comorbidity or hospitalization during baseline if there was evidence of a diagnosis at any time during the baseline period. Evidence of comorbidities or hospitalization during follow-up will be considered as new diagnoses. Once diagnosed, patients will be considered diagnosed for the remainder of their follow-up. ART adherence during baseline and follow-up will be updated every 6 months (180 days) based on the data collected in that previous timeframe. For baseline annual physical exam and annual influenza vaccine, patients will be considered adherent (coded as 'Yes') if there was evidence of these events at any time during the baseline period. During the follow-up, patients will be considered adherent up to 365 days after the last event date.

For annual CD4 and viral load laboratory tests during baseline and follow-up, patients will be coded as 'Yes' up to 365 days after the last event date. For respiratory virus season during follow-up, patients will be coded as 'Yes' if the observation time is in October, November, December, January, February, March or April.

The baseline period for the assessment of covariates is the six months prior to the index date, i.e., no data prior to six months will be included.

Covariates used at baseline only will be considered time-fixed confounders. Covariates additionally or only used during follow-up will be considered time-varying confounders.

Categories may be collapsed, or covariates may be excluded from the propensity scores if models fail to converge.

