Any hospitalization	Evidence of inpatient claim(s) Yes, No	Descriptive, covariate	Baseline and follow-up
Hodgkin's lymphoma	ICD-9-CM or ICD-10-CM codes listed in Protocol Annex 1.11 Yes, No	Descriptive, covariate	Baseline and follow-up
Opportunistic infections	ICD-9-CM or ICD-10-CM codes listed in Protocol Annex Table 14	Descriptive, covariate	Baseline and follow-up

	Yes, No  Note: In the analysis of all-cause pneumonia, pneumocystis jirovecii pneumonia codes are excluded from the follow-up. In the analysis of candidiasis negative control outcomes, candidiasis infection codes are excluded from the follow-up.		
Antiretroviral treatment (ART) adherence	ART use will be identified by NDC codes listed in Appendix Table 7.2  Adherence will be measured as 'Proportion of days covered = (Number of days covered by any ART, excluding ritonavir and cobicistat) ÷ (total days)*100'[8] every six months  Individuals with >80% of days covered will be classified as 'adherent' and individuals with ≤80% of days covered will be classified as 'non-adherent'[8]. Individuals without ART information will be classified as Missing. As a subgroup, ART adherence will be calculated using the information over the entire follow-up.	Descriptive, covariate, subgroup	Baseline and follow-up
CD4 cell count	Categorized as <200, 200-499, ≥500 cells/mm 	Descriptive, subgroup	Baseline and follow-up
PPSV23 vaccination	NDC and CPT codes listed in Appendix Table 7.9  Yes, No. 0, 1, 2+ doses	Descriptive, subgroup	Before first HIV diagnosis, baseline and follow-up
Annual CD4 laboratory test	CD4 laboratory tests will be identified by CPT codes listed in Appendix Table 7.11  Individuals who have at least one CD4 laboratory test performed during each year of follow-up Yes, No	Covariate	Baseline and follow-up
Annual viral load laboratory test	Viral load laboratory tests will be identified by CPT codes listed in Appendix Table 7.12  Individuals who have at least one viral load laboratory test performed during each year of follow-up Yes, No	Covariate	Baseline and follow-up

Respiratory virus season	Respiratory virus season occurs between October 1 and April 30 Yes, No	Covariate	Follow-up
--------------------------	---	-----------	-----------

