#### **5.8.4. Inverse Probability of Treatment Weighting for Time-Varying Exposures**

Except for patients vaccinated more than 13 days before the end of the baseline period, exposure (vaccination) status will not be fixed at start of follow-up, with patients able to receive PCV13 during follow-up. Therefore, PCV13 will be considered a time-varying exposure. The values for some clinical characteristics may also change during the study period and values during baseline may be poor proxies for covariate values at the various points during the follow-up. Therefore, some covariates will be treated as time-varying confounders (Section 5.3.2).

Inverse probability of treatment weighting (IPTW) will be generated from predicted probabilities of vaccination status (propensity scores) to create pseudo-populations where any imbalances in the potential confounders by vaccination status are reduced. For the analyses of first events, stabilized weights will be generated for each patient for the baseline period and every 30 days from index during the follow-up until the earliest of the following: outcome, death, end of health plan enrollment or end of study period. For the analyses of recurrent events, stabilized weights will be generated for each patient for the baseline period and every 30 days from index during the follow-up until the earliest of the following: death, end of health plan enrollment or end of study period. This aims to make vaccination status independent of the measured confounders at each of the follow-up timepoints [9]. The weights will be used to estimate the average treatment effect (ATE). For the analysis of RZV, stabilized weights will be generated every 90 days instead of 30, due to the expected lower numbers of patients vaccinated with RZV overall and in each interval.

The numerators for the stabilized weights will be the estimated probability of a patient's observed vaccination status at timepoint given their prior vaccination status and time-fixed covariates. The denominators will be the estimated probability of a patient's observed vaccination status at the given timepoint given their prior vaccination status, time-fixed covariates and time-varying covariates. Numerators and denominators after vaccination will be set to 1 and the cumulative product of these ratios will be calculated, therefore IPT

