weights after vaccination will be constant. Time-varying covariates will be lagged, i.e., within each 30-day (or 90-day for RZV) interval the vaccination status will be the status at the end of the interval, whereas the values for the covariates will be from the end of the previous interval. Cox proportional hazards models will be used to model the associations between vaccination status and the numerators and denominators.

It is possible that censoring may be informative, with patient characteristics associated with loss to follow-up. Therefore, patients who are censored may have different risks of the study outcomes than patients who are not censored. Inverse probability of censoring weighting (IPCW) will also be generated during the follow-up using the above methods for IPTW. These weights will be multiplied by the IPT weights to produce a new set of weights [9].

Distributions of the IPT, IPC and IPT\*IPC weights will be summarized by vaccination status. In the presence of extreme/outlier weights, stabilized weights may be truncated at the 1st and 99th percentiles for use in the Cox models for the outcomes. Although there is no formal definition of an extreme weight, the need for truncation will be judged based on the distributions and the potential effect on the interpretation of results [9].

Weights for first and recurrent events will be generated separately in datasets created for each study outcome; however, all weights will be derived without assessing their impact on the VE estimates. Weights will also be generated again in each of the subgroups. The weights will be generated using the *ipwtn* function within the *ipw* R package [10]. Example R code is provided in Appendix 7.2.

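### ART adherence is refreshed every 180 days but the weights every 30, so a start or stop of ART can go unrecorded for months and some confounding of VE may remain

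*SAP*

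**What the plan says.** SAP Section 5.3.2 fixes the rhythm of the ART variable: "ART adherence during baseline and follow-up will be updated every 6 months (180 days) based on the data collected in that previous timeframe". Protocol Section 9.3 (Table 1) agrees; its formula for proportion of days covered (PDC) reads "Number of days covered by any ART, excluding ritonavir and cobicistat) ÷ (total days)*100'[27] every six months". SAP Table 5.3 sets the cut-off: "Individuals with >80% of days covered will be classified as 'adherent", and everyone at or below 80% is non-adherent.

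ART adherence enters the weights as a time-varying covariate: "Covariates additionally or only used during follow-up will be considered time-varying confounders" (SAP Section 5.3.2). The weights run on a faster clock. In SAP Section 5.8.4, "stabilized weights will be generated for each patient for the baseline period and every 30 days from index during the follow-up". Vaccination status is read at the end of each interval, "whereas the values for the covariates will be from the end of the previous interval". The censoring weights follow the same method. For the treatment weights only ART status up to vaccination counts, because "Numerators and denominators after vaccination will be set to 1".

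**The concern.** A slow block variable feeds a fast weight model. For the first 180 days of follow-up the ART flag is the baseline value, although SAP Section 5.8.4 itself warns that baseline values may be poor proxies later on.

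Little else in the weights tracks ART going on and off:

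- CD4 count is descriptive and a subgroup variable only (SAP Table 5.3), and only about 25% of the population have any CD4 result (SAP Section 5.2.3).
- The CD4 and viral load covariates record that a test was done, not its result, and stay positive for 365 days.
- Comorbidities and hospitalization stay positive once recorded.

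If people who have just stopped ART are both less often vaccinated and at higher risk of pneumonia, a vaccine with no effect would look protective. The balance check in SAP Section 5.8.5 would not show this, because it tests the same out-of-date flag. Protocol Table 3 expects narrow limits for all-cause pneumonia (2% to 7% around a VE of 5% at 97 months with 4% annual censoring), so a false shift of a few points could look like a precise finding.

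**Working it through.** The plan states no detection delay, so there is no figure of its own to reproduce.

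**1. Delay before the flag changes.** Inputs from the documents: 180-day block, adherent if PDC exceeds 80%, class changed only at a block end. Since 0.80 × 180 = 144, adherence needs at least 145 covered days. Assume continuous cover before a stop or after a start, and let the change fall on day d of a block.

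- Stop: covered days = d − 1. For d ≤ 145 the class changes at this block's end, after 181 − d days (36 to 180). For d ≥ 146 the person still counts as adherent and changes at the next block's end, after 361 − d days (181 to 215). Range 36 to 215 days, mean 125.5.
- Start: covered days = 181 − d. For d ≤ 36 the delay is 181 − d (145 to 180). For d ≥ 37 it is 361 − d (181 to 324). Range 145 to 324 days, mean 234.5.

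The lag adds nothing further. Because 180 = 6 × 30, a value refreshed on day 360 is already the end-of-previous-interval value for days 360 to 390.

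Example: a newly diagnosed person starts ART after 60 days of baseline and misses no dose. Baseline PDC is 120/180 = 67%, so the flag says non-adherent until day 180 of follow-up. A trailing 180-day PDC would reach 150/180 = 83% at day 30.

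**2. Rough size by formula.** Assumed, not in the documents: 5% to 30% per year stop ART; hazard ratio for pneumonia off ART R = 1.5 to 3; vaccination rate ratio off ART h = 0.5 to 1.0.

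- Unrecognised stoppers among those classed adherent: p = rate × 125.5/365.25, which gives 1.7% to 10.3%.
- Their share among the vaccinated: pv = ph/(ph + 1 − p).
- Bias factor on the HR: b = [1 + pv(R − 1)]/[1 + p(R − 1)].
- VE shift = (1 − VE)(1 − b).

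High case (30%, R = 3, h = 0.5): pv = 0.0516/(0.0516 + 0.8969) = 0.0544; b = 1.1087/1.2062 = 0.919; at a true VE of 5% the shift is 0.95 × 0.081 = 7.7 points. With h = 0.8 the range is 0.2 to 3.0 points; with h = 1.0 it is nil.

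**3. Null simulations (true HR = 1).** People move on and off ART in 30-day steps (200,000 people, 60 steps). ART is the only confounder, risk changes at once, and supply data are complete. Scenarios give stop and restart probability per step, relative PCV13 rate off ART, and relative risk off ART. Ranges are from two separately programmed runs (Monte Carlo SE 0.003 to 0.007); single values are from one.

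| Scenario | 180-day block | Trailing PDC | Trailing PDC + supply flag | True status |
|---|---|---|---|---|
| 0.03, 0.06, 0.4, 2 | 0.957–0.973 | 0.965–0.982 | 0.980–1.004 | 0.990 |
| 0.02, 0.04, 0.4, 2 | 0.955–0.968 | 0.964–0.979 | 0.982–0.997 | 0.989 |
| 0.02, 0.04, 0.25, 3 | 0.912–0.926 | 0.929–0.948 | 0.972–0.995 | 0.994 |
| 0.01, 0.05, 0.7, 1.5 (mild) | 0.987 | 0.988 | not run | 0.991 |

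Other mild inputs gave a block HR as close to 1 as 0.993 (trailing PDC 0.995). The higher supply-flag values come from a run in which the flag equals true status by construction.

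- False VE under the block rule: 2.7 points (1 − 0.973) to 8.8 points (1 − 0.912) in the strong scenarios. In the first mild one it is 1.3 points, of which 0.9 remains even with true status.
- Gain from refreshing alone: 0.2 points (0.995 − 0.993) to 2.2 points (0.948 − 0.926).
- Further gain from the supply flag, using the lower values: 1.5, 1.8 and 4.3 points.

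**The case against.** The strongest reply is that nothing here contradicts anything else. Protocol and SAP agree on six-monthly measurement, and ART adherence is adjusted for. Hospitalization and opportunistic infections can switch on at any 30-day boundary. The testing, physical exam and influenza vaccine covariates address engagement in care. Residual confounding by immune status is acknowledged, with negative controls, a CD4 subset analysis and an optional bias correction (SAP Sections 5.2.3 and 5.8.8).

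The simulations also lean one way. The three strong scenarios put a third of people off ART at steady state (for example 0.03/0.09), cut vaccination by 60% to 75%, and double or triple the risk. None of these inputs is in the documents, and omitting the other covariates inflates the residual. In one run even true status gave about 0.99, so up to about 1 point is not due to the flag.

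All of this stands as a limit on size. It does not close the gap: no planned covariate tracks ART interruption and resumption promptly, and a negative control could signal confounding without identifying ART timing as its source.

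A reader might infer more: that confounding by ART use does remain, that the 30-day lag is a fault, or that refreshing the measure would cure the problem. The documents do not support the first, since they give no switching rates or associations of ART change with vaccination or outcome. The lag properly takes covariates from before the interval in which vaccination is read. On the third, a trailing PDC still averages over 180 days, so it needs at least 36 days to register a stop and 145 to register a start.

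**Conclusion.** The mismatch in update frequency is certain from the text. So are the delays of 36 to 215 days for a stop and 145 to 324 days for a start, given continuous cover on either side of the change. That confounding may remain follows; that it does remain, or how much, cannot be shown.

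Under assumed inputs and with no other covariates, false VE runs from about 1 point or less (mild) to about 3 to 9 points (strong), and is nil if recent ART change does not affect vaccination. The expected all-cause pneumonia VE is 5% to 15% (Protocol Section 9.5), so the upper part of that range would matter. This is a correctable weakness in the main HIV-specific time-varying covariate. It does not invalidate the design.

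**What to change.** In SAP Section 5.3.2 and Table 5.3, compute PDC over the trailing 180 days at each 30-day boundary (90-day for RZV), keeping the 80% cut-off. Add a yes/no covariate for ART supply on hand at that boundary. Use both in the denominators of the treatment and censoring weights, and align the six-monthly wording in Protocol Section 9.3. If the six-monthly rule stays primary, prespecify this version as a sensitivity analysis reported beside it.

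The work is SAP wording and a rolling calculation on dispensing data already held. There are three drawbacks:

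- The weights become slightly more variable.
- Fills not captured in the claims would be read as off ART, since Protocol Section 9.8 treats absent data as absence.
- Two overlapping ART terms may make convergence harder, and SAP Section 5.3.2 allows covariates to be dropped for that reason. The SAP should therefore say which ART term is kept.

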9.2. Setting

Health care administrative claims and laboratory data will be provided by Komodo Health. Komodo Health uses artificial intelligence and data analytics to combine and link patient-level information from more than 150 payers in the United States, including Medicare, Medicaid, and Commercial plans.

Komodo Health will provide administrative claims data and HIV-related laboratory data available during January 1, 2014 through September 30, 2022 for individuals who have at least one ICD-9-CM or ICD-10-CM code related to HIV (Appendix Table 1) or at least one ART medication dispensed (Appendix Table 2).

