### 5.2.2. Exclusion Criteria

*Patients meeting the following criterion will not be included in the study:*

1. *Evidence of PCV13 vaccination before the first HIV-related ICD-9-CM or ICD-10-CM code*

All available data prior to first HIV-related ICD-9-CM or ICD-10-CM code will be used to assess evidence of PCV13 vaccination, however there is no minimum time requirement.

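### Baseline influenza vaccination is read from six months only, so its value depends on the calendar month of the first HIV code

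*SAP*

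**What the plan says.** SAP 5.1 starts the six-month baseline at the first HIV code and sets index on the day after it ends. SAP 5.3.2 limits baseline covariates to "the six months prior to the index date, i.e., no data prior to six months will be included". Influenza vaccine and physical exam are 'Yes' at baseline only "if there was evidence of these events at any time during the baseline period". Later the rule is longer: "During the follow-up, patients will be considered adherent up to 365 days after the last event date". The laboratory tests have a 365-day rule at both stages: "For annual CD4 and viral load laboratory tests during baseline and follow-up, patients will be coded as 'Yes' up to 365 days" after the last test. The six-month bar prevents that rule from working in full at baseline.

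Protocol 9.8 treats a missing code as absence of the event, so an unseen dose becomes 'No', not unknown. Influenza vaccine is used at baseline and in follow-up, and "Covariates additionally or only used during follow-up will be considered time-varying confounders". It therefore enters the weight denominator. SAP 5.8.7 carries only the time-fixed covariates into the outcome model, although SAP 5.8.5 allows variables still imbalanced after weighting to be added. Under SAP 5.8.4 time-varying covariates are lagged by one interval and the treatment weight is constant after PCV13.

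Earlier claims are used elsewhere. For the exclusion, "All available data prior to first HIV-related ICD-9-CM or ICD-10-CM code will be used to assess evidence of PCV13 vaccination" (SAP 5.2.2), and SAP Table 5.3 counts PPSV23 doses from before the first HIV diagnosis.

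**The concern.** Influenza vaccination is seasonal and the baseline window covers half a year. Two people with the same habit, vaccinated every autumn, can be coded oppositely because one has a first HIV code in February and the other in July. Month of entry is not among the covariates in SAP Table 5.3. The calendar terms are year of first HIV code and an October-April indicator used in follow-up only.

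SAP 5.8.8 names inadequate control for health-care seeking as a source of residual confounding, and influenza vaccination is one of the plan's few markers of it. Where the marker is miscoded, the weights cannot balance the habit behind it. The standardized differences in SAP 5.8.5 would not reveal this, because they are computed on the same miscoded variable.

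**Working it through.** The plan gives no figure for this point, so there is none to reproduce. The check applies the SAP rule to a person vaccinated at the same time every year.

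**Inputs.** Baseline starts at the first HIV code and lasts six months (SAP 5.1, 5.3.2). It is taken as 180 days where days are needed, as SAP 5.3.2 does for ART adherence. *Assumption:* dose timing, which the documents do not give.

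**Step 1: detection under even September-December dosing.** Detection = (months of September-December inside the window) / 4, with the window starting on the 1st. For April the window is April-September, so 1/4 = 25%.

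**Step 2: other timings.** The first code is spread evenly within each month, the window is 180 days, and there are five patterns: even over September-October, September-November, September-December and August-January, and a September-January pattern peaking in October. The last column is the simulated range of every-year vaccinees coded 'No'.

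| Month of first HIV code | Detected, step 1 | Coded 'No', step 2 |
|---|---|---|
| January | 0% | 92-100% |
| February | 0% | 93-100% |
| March | 0% | 77-92% |
| April | 25% | 31-66% |
| May | 50% | 0-44% |
| June | 75% | 0-27% |
| July | 100% | 0-11% |
| August | 100% | 0-9% |
| September | 100% | 10-25% |
| October | 75% | 37-75% |
| November | 50% | 58-100% |
| December | 25% | 75-100% |

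Mean of the step 1 column: (25 + 50 + 75 + 3 × 100 + 75 + 50 + 25) / 12 = 600 / 12 = 50%. In step 2 the share coded 'No', averaged over months, is 51% for every pattern, which is 1 − 180/365.

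**Step 3: measures without a season.** An exam or test done once a year and spread evenly is missed at baseline with probability 1 − 180/365 = 51%, whatever the entry month.

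**Step 4: how long the error lasts.** With entry spread over the year, a miscoded annual vaccinee has the next dose somewhere in the 185 days after index, on average at 92.5 days. Over all annual vaccinees, miscoded time is 0.507 × 92.5 ≈ 47 days, or 47/365 ≈ 13% of the first year. For first codes in December to February the mean time to correction is 48 to 131 days, by month and pattern. The lag adds up to one 30-day interval before the weight model sees the new value. SAP 5.3.2 does not say whether the last event in the follow-up rule may precede baseline; if it may, correction comes sooner.

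**Step 5: who keeps the error.** For PCV13 given during baseline, the treatment weight is built from baseline values and is then constant. For PCV13 in follow-up before the next influenza dose is seen, the miscoded value enters the weight at vaccination and is not revised.

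**Step 6: what a longer look-back can reach.** Protocol 9.2 gives claims and "HIV-related laboratory data available during January 1, 2014 through September 30, 2022". A first code in January 2014 has at most 30 earlier days of data, and one in June 2014 at most 180. Neither reaches autumn 2013. For later first codes a 365-day window up to index contains one dose of an every-year vaccinee, provided the claims exist. No enrolment before the first code is required.

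**The case against.** The best defence is that the error is short-lived. Influenza vaccine is time-varying and weights are updated every 30 days, so the next dose corrects the code. That stands for most people, but not for those whose weight is already constant.

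A fixed window also gives everyone the same ascertainment, whereas look-back would differ with prior enrolment. That is a fair reason for the choice. But equal length is not equal ascertainment for a seasonal event, as the table shows.

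The plan has other health-seeking covariates (exam, CD4 and viral load testing, ART adherence), and it has negative controls. The covariates may absorb part of the confounding. The negative controls detect residual confounding but do not remove this miscoding. The RZV analysis leaves out people with RZV in baseline (SAP 5.8.8), and candidiasis is proposed for immune status. The season indicator carries some entry-season information at a given time since index, but it is not used at baseline, where many of the lasting weights are set.

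A reader might infer three stronger things that the documents do not support:

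- **Everyone entering in winter or spring is miscoded.** April and May first codes are only partly affected, and October to December codes are affected too. By index date the pattern moves six months, so summer index dates are the ones mostly missed.
- **A large group has first codes in early 2014, when detection is near zero.** Prevalent cases are eligible and claims start then, so this is plausible, but no distribution of entry months is given.
- **VE is biased upward by a known amount.** One can assume 40% annual vaccinees among people without PCV13, odds ratios of 1.5 to 3 between the habit and PCV13, and hazard ratios of 0.90 to 0.80 for pneumonia. If the habit is wholly unmeasured, this gives 1 − 0.95/0.96 = 1.0 point to 1 − 0.867/0.92 = 5.8 points. None of these inputs is in the documents. The figure is a worst case for people vaccinated in baseline and cannot be set against the overall VE of 5-15% assumed in Protocol 9.5.

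**Conclusion.** The point holds in a limited form. For influenza vaccine, the baseline value depends strongly on the month of the first HIV code: under even September-December dosing, detection runs from 0% to 100% and averages 50%. The ends of that range are robust to the assumed timing (January-February codes 92-100% 'No', July-August codes at most 11%); the months between are not. The other annual items lose about half of once-a-year users at baseline without a link to entry month, if they are evenly spread over the year.

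The lasting effect is confined to people given PCV13 in baseline or in follow-up before the next influenza dose. The documents do not give their number, and they support neither a size nor a direction for bias in VE. The change is still worth making, because a stated rule weakens a confounder the plan relies on and the repair uses data already held.

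**What to change.** In SAP 5.3.2 and Table 5.3:

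1. Measure influenza vaccine, physical exam, CD4 and viral load tests over the 365 days up to index where claims exist. State whether the follow-up 365-day rule may count events before baseline. This also reconciles the laboratory-test rule with the six-month bar.
2. Give influenza vaccine a third level, 'vaccination season not observed', where claims do not cover the season. This fits SAP 5.7, which analyses unknown values as their own category.
3. Add calendar quarter of index as a time-fixed covariate in the numerator, denominator and outcome models.
4. State as a limitation that first codes in early 2014 have no data for autumn 2013. Look-back cannot recover their status, so confounding by vaccination habit remains in that group.
5. Keep the six-month definition as a sensitivity analysis.

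The cost is SAP wording, a few derived variables and a few parameters (three for quarter, one for the extra level). The drawback is that look-back length will vary between people. The third level makes this visible for influenza vaccine, and the sensitivity analysis shows whether it matters.
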